4.2.4.3 Drug-induced liver injury

Number and percentage of patients meeting potential Hy's laws criteria (aspartate aminotransferase [AST] or alanine aminotransferase [ALT] $\geq 3x$ upper limit of normal [ULN] and total bilirubin [TB] $\geq 2x$ ULN) at any point during the Treatment period or follow-up period will be presented in a summary table by visit and treatment group for Safety analysis set. Similarly, a table with key patient data for patients with combined ALT or AST, and TB, elevations will be presented.

4.2.4.4 Clinical laboratory

Continuous clinical laboratory parameters will be summarized in standardized international (SI) and US conventional units.

For quantitative measurements, observed values and changes from baseline to each post-baseline visit will be determined by visit windows described in Section 4.3.1 and 4.3.3.

All hematology, clinical chemistry, growth and development hormones and urinalysis results will be listed by treatment group, patient, and visit, including scheduled and unscheduled/repeat measurements. Laboratory assessments that are outside of normal ranges will be flagged.

Baseline values, the observed values at each visit to Week 52 and including the 10-week follow-up, as well as change from baseline values will be summarized for each of the quantitative laboratory assessments by treatment group. Additionally, listings by individual patients' data will be reported as appropriate.

Clinical laboratory results (chemistry, hematology, growth and development hormones and urinalysis) will be summarized using descriptive statistics for each visit. Shift from baseline to the minimum/maximum value during treatment will be presented for the controlled assessment period and extension period, separately, based on high/low/normal findings for clinical laboratory parameters if normal ranges are available (for quantitative measurements and categorical measurements). For the categorical Urine-Blood parameters, a shift table from baseline to every planned visit will be performed. For the categorical measurements Urine Glucose, Ketones and Urine Total Protein, results will be presented under the following categories: 0, trace, +1, +2, +3.

Number and percentage of laboratory results that are potentially clinically significant (see [Appendix B3](#)) will be summarized by analyte name and criteria for each treatment group.

Estimated glomerular filtration rate will be derived based on the Bedside Schwartz formula:

$$eGFR = 41.3 * (\text{Height in meters} / \text{Serum creatinine in mg/dL})$$

A table of observed and change from baseline in eGFR values will be provided. This will be provided both overall and by baseline eGFR, hyperfiltrating versus non-hyperfiltrating, where hyperfiltration is defined as an $eGFR \geq 125 \text{ ml/min/1.73m}^2$.

A MMRM analysis of change in eGFR from baseline to Week 24 and each intermediate visit by baseline eGFR (hyperfiltrating: $\geq 125 \text{ ml/min/1.73m}^2$ versus non-hyperfiltrating: $< 125 \text{ ml/min/1.73m}^2$) will be provided. The same approach as stated in Section 4.2.3.3 will be used. The model will include treatment group, visit, interaction between visit and treatment, region, screening HbA1c strata ($< 9.0\%$, $\geq 9.0\%$), baseline eGFR, and interaction between visit and baseline eGFR as the fixed effects. The REML method will be used for parameter estimation. The least squares mean, 2-sided 95% confidence interval, and p-value of the difference in the endpoints of interests between the EQW and PBO groups will be presented. This analysis will be done both excluding data after initiation of rescue therapy and separately including data after initiation of rescue therapy.

A shift table from baseline UACR category to highest post-baseline UACR category will be provided for the controlled assessment period and extension period, separately. Categories are defined as follows:

- $< 30 \text{ mg/g}$ (Normal)
- $\geq 30 \text{ mg/g}$ and $\leq 300 \text{ mg/g}$ (Micro or moderately increased albuminuria)
- $> 300 \text{ mg/g}$ (Macro or severely increased albuminuria)
- Unknown

Strip Sign for Selected Laboratory Data

For selected laboratory test values that have been received with a qualifier as a part of the result ($>$, \geq , $<$, or \leq), a process to strip the qualifier will be applied and the resulting numeric

values will be used for data analysis. The raw value with operator will remain as such in the database and will be used when listed.

4.2.4.5 Vital signs

Vital signs (systolic and diastolic blood pressure and heart rate) will be summarized by visit and treatment group. Observed and change from baseline values will be summarized for each visit where appropriate. This summary will be repeated by age group (<12 years, ≥12 years).

Number and percentage of vital signs that are potentially clinically significant (see [Appendix B3](#)) will be summarized by parameter, category treatment group and age group (<12 years, ≥12 years). Individual patient data for patients with marked abnormality criteria will be summarized.

Vital signs parameters will be listed.

4.2.4.6 Antibodies to exenatide

A patient is said to have treatment emergent antibodies to exenatide at a visit if the antibody test is positive after the first injection of study medication following a negative or missing antibody measurement prior to the first injection of study medication, or the titer is increased by at least 3 dilutions from a detectable measurement prior to the first injection of study medication.

Number and percentage of patients incidence of antibodies to Exenatide for the categories negative, any positive, low positive, and high positive will be summarized descriptively by visit for the safety analysis set, for the treatment period.

The primary efficacy endpoint HbA1c will be summarized by antibody status (negative, any positive, low positive, higher positive) and by visit to evaluate the effect of antibody formation on efficacy.

Descriptions of planned summaries of AEs by antibody status can be found in [Section 4.2.4.1](#). Antibodies to exenatide will be defined based on the highest antibody titer in each patient at any time during the on-treatment period.

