5.4 Blinding and procedures for unblinding the study

5.4.1 Methods for ensuring blinding

The Sponsor, the study-site personnel, and the patients will be blinded to treatment allocation during the double-blind controlled assessment period. Every effort should be made to ensure that patients remain blinded to their treatment during this period.

The exception to the above is for those personnel analyzing the PK and antibody samples. The randomization information will be provided to ensure that only samples from patients who were on active study treatment are analyzed. Samples from patients not dosed with the relevant active study treatment will only be analyzed on a “for cause” basis, for example, if there is suspicion that a patient has been dosed incorrectly.

During the open-label extension period, the Sponsor, study-site personnel, and the patients will be unblinded to the identity of the study medication.

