6.2.3.7 Visit 7 (Week 24) – (Controlled assessment period)

Prior to Visit 7 (Week 24), patients will have fasted overnight (≥ 8 hours). If the study visit is scheduled on the same day as the patient's weekly administration of study medication, patients should delay administration of study medication on the morning of the study-site visit and bring the study medication to the site.

All patients will undergo the following procedures:

- Review of concomitant medication and AEs
- Body weight, height, and vital signs will be measured
- Urine will be collected for:
 - Pregnancy test (females only)
 - Urinalysis
 - N-telopeptide.
- Assessment of Tanner pubertal stage
- Injection site reaction assessment will be performed
- Blood samples will be collected for:
 - Chemistry and hematology
 - HbA1c
 - Fasting plasma glucose
 - Fasting insulin
 - Fasting lipids (TC, HDL-C, LDL-C, and TG)
 - TSH, FSH, LH, total testosterone, SHBG, estradiol, free T4, prolactin, cortisol, IGF-1, DHEAS, and bone specific alkaline phosphatase
 - Measurement of antibodies to exenatide
 - Measurement of plasma exenatide.
- Patients will receive diet and nutritional counseling
- Patients will have a study medication compliance review

- Study medication will be dispensed
- Patient and/or parent/caregiver will administer study drug at the study site (if applicable)
- Patients will be asked to return used/unused study medication.

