Antibodies to exenatide

Blood samples will be collected for the measurement of antibodies to exenatide according to the schedule presented in the Study Plan (Table 1, Section 6.2). Samples for determination of anti-exenatide antibodies will be analyzed by a selected laboratory on behalf of AstraZeneca, using an appropriate method.

Only samples from patients who were on active study treatment will be analyzed. Samples from patients not dosed with the relevant active study treatment will only be analyzed on a “for cause” basis, for eg, if there is suspicion that a patient has been dosed incorrectly.

The method details and results will be reported in a separate report appended to the CSR. Anti-exenatide antibody samples received by the analytical group will be disposed of after the anti-exenatide antibody report finalization or 6 months after issuance of the draft antibody report (whichever is earlier), unless requested for future analyses or in support of the development or conduct of the assay.

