12.6.7.2 Clinical laboratory evaluations

All hematology, clinical chemistry, and urinalysis results will be listed by treatment, patient, and visit, including scheduled and unscheduled/repeat measurements. Laboratory assessments that are outside of normal ranges will be flagged.

Baseline values, the values at each visit, and changes from baseline values will be summarized for each of the quantitative laboratory assessments by treatment.

Shift tables of hematology, clinical chemistry, and urinalysis results will be used to summarize changes from Baseline Visit 2 (Week 0) to Study Termination (Visit 11 [Week 62] or Early Termination), and to each intermediate visit.

Antibody to exenatide data will be listed and summarized. A shift table of antibodies to exenatide will be used to summarize the change from baseline Visit 2 (Week 0) to each scheduled measurement. A patient is said to have treatment-emergent antibodies to exenatide at a visit if the antibody test is positive after the first injection of study medication following a negative or missing antibody measurement prior to the first injection of study medication, or the titer is increased by at least 3 dilutions from a detectable measurement prior to the first injection of study medication. The incidence of treatment-emergent antibodies to exenatide will be summarized by study visit, as appropriate.

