3.4 Safety variables

- Corresponding to the primary safety objective, safety and tolerability endpoints including the incidence of treatment emergent AEs (TEAEs; see section 4.2.4.1), antibodies to exenatide, physical examinations, laboratory measurements (clinical, chemistry/hematology), and vital sign measurements from baseline Visit 2 (Week 0) to Visit 7 (Week 24), Visit 10 (Week 52), and to each intermediate visit as applicable
- Proportions of patients reporting different injection site reactions at Visit 3 (Week 4) through Visit 10 (Week 52) (see Section 4.2.4.2 for details of injection site reaction reporting)
- Change in calcitonin, pancreatic amylase, and lipase from baseline Visit 2 (Week 0) to Visit 5 (Week 12) and Visit 10 (Week 52)

- Change in Thyroid-stimulating hormone (TSH), thyroxine (free T4), prolactin, cortisol, insulin-like growth factor 1 (IGF-1), and Dehydroepiandrosterone (DHEAS) from baseline Visit 2 (Week 0) to Visit 5 (Week 12), Visit 7 (Week 24), and Visit 10 (Week 52)
- Tanner pubertal stage at baseline Visit 2 (Week 0), Visit 5 (Week 12), Visit 7 (Week 24), Visit 9 (Week 40), and Visit 10 (Week 52)

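### Treatment-emergent antibodies are counted from the first study injection, which is placebo for Group B, and a missing pre-dose result is treated as negative, so switchers' status before EQW is ignored

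*SAP*

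**What the plan says.** - **Sampling.** The visit lists in Protocol 6.2.3 draw antibody blood from all patients at Weeks 0, 4, 8, 12, 24, 52 and 62. The Week 24 list, for example, includes "Measurement of antibodies to exenatide" with no restriction by arm.
- **Assay.** Protocol 6.4.5.5: "Only samples from patients who were on active study treatment will be analyzed". It continues: "Samples from patients not dosed with the relevant active study treatment will only be analyzed on a" for-cause basis, such as a suspected dosing error. Protocol 5.4.1 explains how the selection is made: "The randomization information will be provided to ensure that only samples from patients who were on active study treatment are analyzed".
- **Definition.** SAP 4.2.4.6 and Protocol 12.6.7.2 give the same two-part rule. A positive is treatment-emergent either when it comes "following a negative or missing antibody measurement prior to the first injection of study medication", or when "the titer is increased by at least 3 dilutions from a detectable measurement prior to the first injection of study medication".
- **Design.** Group B receives placebo for 24 weeks and then EQW for 28 weeks (Protocol synopsis). SAP 3.6.1 keeps the Week 0 baseline for change-from-baseline summaries in the extension, and SAP 4.2.4.6 sets no separate reference point for the switch.
- **Outputs.** Protocol 12.6.7.2 plans an antibody shift table from Week 0 to each scheduled measurement and adds: "The incidence of treatment-emergent antibodies to exenatide will be summarized by study visit, as appropriate". SAP Section 5, which lists departures from the protocol, withdraws neither. SAP 4.2.4.6 itself tabulates negative, any positive, low positive and high positive by visit.
- **Status of the variable.** SAP 3.4 puts antibodies to exenatide in the item that begins "Corresponding to the primary safety objective, safety and tolerability endpoints including the incidence of treatment emergent AEs". That objective compares EQW with placebo at 24 weeks.

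**The concern.** The definition asks what changed after exposure to study drug. For Group B the clock starts at a placebo injection, and the result that should serve as the reference is, on the likely reading, never produced. Treating missing as negative then decides the classification. A switcher who already reacted in the assay before any EQW is recorded as having developed antibodies on EQW. The same rule works differently in Group A, where a Week 0 result exists and a patient positive before dosing must show a titer rise to count.

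At stake is how the immunogenicity data are read. The treatment-emergent incidence among switchers would be inflated by any pre-existing or non-specific reactivity. The controlled-period comparison that the safety objective calls for would also have EQW results with no placebo results beside them.

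**Working it through.** The documents state no antibody rate, assay specificity or cut-point, so there is no figure of the plan's own to reproduce. The check is mainly a reading of the rules, with one illustrative calculation.

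**Step 1: apply the rules to each group.**

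| | Group A (EQW throughout) | Group B (placebo, then EQW) |
|---|---|---|
| First study injection | EQW, Week 0 | Placebo, Week 0 |
| Week 0 sample assayed? | Yes | No, except for cause (natural reading) |
| Weeks 4, 8, 12, 24 assayed? | Yes | No, except for cause (natural reading) |
| Result before first injection | Available | Missing |
| Positive on or after EQW | Depends on the Week 0 result | Always treatment-emergent |
| Titer-rise criterion | Can apply | Cannot apply: it needs a detectable pre-dose result |
| Week 0 shift table | Can be filled | Cannot be filled |

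Group B's draws after the switch are at Weeks 52 and 62.

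**Step 2: test the other reading.** Protocol 6.4.5.5 describes patients, not samples. Every Group B patient who enters the extension is eventually dosed with EQW, so one could argue that their stored Week 0 to 24 samples are also assayed. The Week 0 result would then exist. But a patient negative at Week 0 and positive at, say, Week 12 on placebo would count as having treatment-emergent antibodies before any exposure to EQW. The reference point is therefore wrong for Group B on either reading.

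**Step 3: size.** Inputs: 77 randomized 5:2 (Protocol 12.7), and a background positive rate *f*, which the documents do not give. I assume 1% to 5%.

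- Group B: 77 × 2/7 = 22. Group A: 77 × 5/7 = 55.
- Expected switchers misclassified, if background reactivity persists within a patient: 22 × *f* = 22 × 0.01 = 0.22, to 22 × 0.05 = 1.1.
- Chance of at least one: 1 − (1 − *f*)^22 = 1 − 0.99^22 = 20%, to 1 − 0.95^22 = 68%.
- If background positives were instead independent at the two post-switch draws: 22 × [1 − (1 − *f*)²] = 0.44 to 2.15.

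These figures use all 22 planned patients and ignore dropout before the switch.

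**The case against.** Several points on the other side are sound.

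- **The non-assay of placebo samples is not stated beyond doubt.** The patient-level reading in Step 2 is possible, and the planned Week 0 shift table fits it. Selection by randomization information in Protocol 5.4.1 fits the other reading better, but the text should settle it. This weakens the claim about missing results; it leaves the problem with the reference point.
- **A reader might infer that the EQW arm's positivity has no background to be read against.** The documents do not support that. About 55 EQW patients have a Week 0 sample taken before dosing and eligible for assay. Because the arms are randomized, it estimates pre-existing reactivity in the same population. What is missing is narrower: a concurrent placebo result, and Group B's own status before EQW. Prior exenatide or other GLP-1 receptor agonist use is also an exclusion (Protocol 4.3, criterion 7), so earlier drug exposure should not be a source of background.
- **A reader might compound the background over the EQW arm's five on-treatment draws** and get 1 − 0.99^5 = 4.9% to 1 − 0.95^5 = 22.6% ever positive by chance. That needs independent samples as well as an assumed rate. Pre-existing reactivity would tend to persist, and with full persistence the figure stays at 1 to 5%.
- **Few outputs depend on the flag.** The SAP's own antibody table uses positive, negative and titer categories. The immune-related adverse event tables (SAP 4.2.4.1) use status and titer, based on the highest on-treatment titer. Treatment-emergent incidence and the shift table come only from Protocol 12.6.7.2. Extension summaries label switchers separately (SAP 4.1.1), so they are not pooled unseen with the EQW arm.
- **Counting missing as negative errs toward over-reporting,** which is the cautious direction for safety. That is fair, but over-reporting in one group only still distorts the comparison between groups.

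**Conclusion.** The point holds in a limited form. The definition takes the wrong reference injection for Group B. On the most natural reading of the assay restriction, it also makes every positive after the switch treatment-emergent regardless of status before EQW. The titer-rise criterion and the Week 0 shift table then cannot work for Group B, and a safety variable tied to the EQW-versus-placebo objective has no concurrent placebo result.

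The numerical effect is small, about 0.2 to 1.1 of 22 switchers. It rests on an assumed background of 1 to 5%, persistence within patients and no dropout before the switch. It is confined to descriptive safety outputs: no efficacy or hypothesis-testing result depends on it. The definitional fault does not depend on the assumed rate.

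**What to change.** 1. In SAP 4.2.4.6, define treatment-emergent relative to the first injection of EQW, with the last sample before EQW as the reference. For Group B that is the Week 24 pre-dose sample. Record this as a change from Protocol 12.6.7.2.
2. Amend Protocol 5.4.1 and 6.4.5.5 to state that Group B's stored Week 0 and Week 24 samples are assayed once the controlled period is unblinded. That protects the blind.
3. Show placebo positivity at Week 24 beside EQW positivity at Week 24.
4. Report positives with no pre-EQW result as a separate category instead of counting them as treatment-emergent.

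The cost is about 22 × 2 = 44 extra assays and wording changes in both the SAP and the protocol. No new visits or blood draws are needed, because the samples are already scheduled. The assays depend on the samples still being available: Protocol 6.4.5.5 allows disposal once the antibody report is final or 6 months after its draft, whichever is earlier, so the decision must come before then. If the samples are gone, items 1 and 4 can still be done.

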AE will be considered as possibly-related to study medication; for missing seriousness, the AE will be considered serious.

On-treatment AEs (TEAEs) will be summarized for 24-week controlled assessment period and 28-week extension period as defined below. Off-treatment AEs for treatment completers to Week 52 will be tabulated where required. Off-treatment AEs for patients who prematurely discontinued will be listed only.

An overall summary of number and percentage of patients experiencing at least 1 TEAE will be presented for EQW and PBO. The summary will be presented by study period (controlled assessment period and extension period). A summary of AEs during the Treatment period for patients with actual treatment EQW during the controlled assessment period will be provided. The AE summary will include the number and percentage of patients experiencing any AE, any SAE, any AE related to treatment per Investigator's discretion, any AE leading to treatment discontinuation, any AE leading to study withdrawal, and any fatal AE.

Additionally, all TEAEs will be summarized for each treatment group as follows:

- AEs summarized by SOC, PT, maximum intensity (Mild, Moderate, Severe), causality (Not related, Related), action taken, and outcome.
- SAEs summarized by SOC and PT, maximum intensity (Mild, Moderate, and severe), causality (Not related, Related).
- AEs leading to treatment discontinuation summarized by SOC and PT.
- Frequent AEs (AE with at least 5% incidence in any treatment) summarized by preferred term.
- Non-serious frequent AEs summarized by SOC and PT.
- Potentially immune-related AEs summarized by antibody status (positive versus negative), SOC and PT.
- Potentially immune-related AEs summarized by antibody titer (higher: ≥ 625 versus low: < 625), SOC and PT.
- Potentially immune-related injection site-related AEs summarized by SOC and PT.

Summaries by maximum intensity will be presented separately for the controlled assessment period (Safety analysis set) and extension period (subset of Safety patients who received open-label EQW during the extension period). All other AE summary tables will be presented by study period in a single table.

Potentially immune-related AEs will be identified using the PTs given in [Appendix B4](#).

Injection site-related AEs will be identified using AEs within higher-level term "Injection site reactions".

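### The SAP defines treatment-emergent exenatide antibodies but plans no output that uses the definition, and it drops the protocol's baseline shift table without declaring either change

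*SAP*

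**What the plan says.** Protocol 12.6.7.2 commits to two displays that refer back to the pre-dose sample. The first is an incidence: "The incidence of treatment-emergent antibodies to exenatide will be summarized by study visit, as appropriate". The second carries no qualifier: "A shift table of antibodies to exenatide will be used to summarize the change from baseline Visit 2 (Week 0) to each scheduled measurement".

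SAP 4.2.4.6 carries over the protocol's two-part definition. A patient has treatment-emergent antibodies if "the antibody test is positive after the first injection of study medication following a negative or missing antibody measurement prior to the first injection", or if "the titer is increased by at least 3 dilutions from a detectable measurement prior to the first injection of study medication".

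The table that follows is different: "Number and percentage of patients incidence of antibodies to Exenatide for the categories negative, any positive, low positive, and high positive will be summarized". The section's only rule for assigning a patient's status is this: "Antibodies to exenatide will be defined based on the highest antibody titer in each patient at any time during the on-treatment period".

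Two further summaries depend on antibody status. In the same section, "The primary efficacy endpoint HbA1c will be summarized by antibody status", with the aim of judging how antibody formation affects efficacy. SAP 4.2.4.1 adds "Potentially immune-related AEs summarized by antibody status (positive versus negative), SOC and PT", and a companion table split at a titer of 625.

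The shift tables in SAP 4.2.4.4 cover the clinical laboratory panels and the urinary albumin-creatinine categories, not antibodies. SAP Section 5, which lists departures from the protocol, mentions neither the treatment-emergent incidence nor the antibody shift table. The SAP amendment history records only a wording alignment for 4.2.4.6.

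**The concern.** Antibodies to exenatide are named among the endpoints tied to the primary safety objective (SAP 3.4), and that endpoint is framed as running from baseline. The useful question is how many patients develop antibodies, or show a material rise, after starting the drug. Both documents provide for patients with a detectable result before the first injection and count them only if the titer rises by at least 3 dilutions. The planned SAP tables make no such separation. Without the shift table, a reader of the study report could not tell new positives from carried-over ones at any post-baseline visit.

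The HbA1c summary has the same difficulty. It is meant to speak to antibody formation, yet its positive groups do not require that anything formed after dosing began.

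**Working it through.** **Comparison of the two plans**

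| Item | Protocol 12.6.7.2 | SAP 4.2.4.6 |
|---|---|---|
| Treatment-emergent definition | Given | Given, in the same terms |
| By-visit incidence | Treatment-emergent, where appropriate | Negative, any, low and high positive |
| Pre-dose condition in the table | Yes, through the definition | None stated |
| Patient-level status | Not set | Highest on-treatment titer |
| Shift table from Week 0 | Yes, unconditional | None |
| Declared in SAP Section 5 | – | No |

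**One patient under both rules.** Take a patient with a detectable titer at Week 0 who stays positive on treatment with a rise of less than 3 dilutions.

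- First limb of the definition: fails, because the pre-dose result is neither negative nor missing.
- Second limb: fails, because the rise is too small. The patient is not treatment-emergent.
- SAP categories: the patient is any-positive, and also low or high positive by titer. The same status carries into the HbA1c and adverse event summaries.

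A by-visit table might include a Week 0 row showing how many patients were positive before dosing. It would not show which of the later positives they are.

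**Possible size.** The documents state no antibody rate, so there is no plan figure to reproduce. Inputs:

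- 77 randomized at 5:2 (protocol synopsis), so 77 × 5/7 = 55 exenatide patients.
- p, the proportion positive before dosing. It is not in the documents; 2%, 5% and 10% are assumed.
- s, the proportion of those patients with a rise of at least 3 dilutions. It is not in the documents; 0 and one half are assumed.
- c, the conversion rate among patients negative before dosing. It is also not given.
- All pre-dose positives are assumed to stay positive on treatment.

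Any-positive proportion = (1 − p)c + p. Treatment-emergent proportion = (1 − p)c + ps. The gap is p(1 − s), which does not depend on c. The chance of at least one pre-dose positive among 55 is 1 − (1 − p)^55.

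| p | Expected pre-dose positives, 55p | Chance of at least one | Gap, s = 0 (points) | Gap, s = 0.5 (points) |
|---|---|---|---|---|
| 2% | 1.1 | 0.67 | 2.0 | 1.0 |
| 5% | 2.75 | 0.94 | 5.0 | 2.5 |
| 10% | 5.5 | >0.99 | 10.0 | 5.0 |

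For illustration, with c = 50% and s = 0 the treatment-emergent and any-positive figures would be 49.0% and 51.0%, 47.5% and 52.5%, or 45.0% and 55.0%. The s = 0 column is the upper limit for each p.

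**The case against.** **The definition may be meant to govern the table.** It stands directly before the table sentence, and that sentence speaks of incidence. The authors may have intended this, but the category labels do not say so and the highest-titer rule has no pre-dose condition. If that was the intent, the SAP should state it.

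**The protocol leaves room.** Its incidence summary is to be done only as appropriate, and a table labelled any-positive reports positivity under its own name. That softens the first omission. It does not touch the shift table, which the protocol promises without condition.

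**Few patients may be affected.** Exclusion criterion 7 (protocol 4.3) bars anyone who has ever used exenatide or another GLP-1 receptor agonist, which removes the obvious source of pre-existing antibodies. Samples are analyzed only from patients on active treatment, except for cause (protocol 5.4.1 and 6.4.5.5). Where a placebo patient's Week 0 sample was not analyzed, the pre-dose result is missing and a later positive is treatment-emergent by definition, so the two classifications agree. Both facts stand and narrow the affected group. SAP 4.1.1 also plans individual listings, through which single cases could be traced.

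**The tempting stronger readings.** A reader might infer that the reported incidence will be inflated by pre-existing reactivity. The documents do not support that as a fact: they give no baseline positivity, and if no patient is positive before dosing the two counts are identical. A reader might also infer that the HbA1c and adverse event tables should switch to treatment-emergent status. The protocol plans no such tables by antibody status, so the SAP breaks no commitment there, and on-treatment positivity is a defensible grouping for immune-related events. A plain switch would also move pre-dose positives without a titer rise into the negative comparison group.

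**Conclusion.** The gap between the documents is established from the text alone. No planned SAP output uses the treatment-emergent definition, the protocol's unconditional antibody shift table is missing, and Section 5 declares neither change.

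Whether any count is affected depends on pre-dose positivity, which is unknown and may be low. Under the assumed 2%, 5% and 10%, with every pre-dose positive staying positive and none rising by 3 dilutions, at most about 1.1, 2.8 or 5.5 of some 55 exenatide patients would be any-positive without being treatment-emergent. These tables are descriptive. The primary HbA1c analysis and the testing hierarchy are untouched. The point still merits correction because it concerns an endpoint under the primary safety objective and the data needed are already collected.

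**What to change.** In SAP 4.2.4.6:

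- Add the number and percentage of patients with treatment-emergent antibodies by visit, using the definition already there, and keep the any-positive, low and high rows alongside.
- Restore the shift table from Week 0 to each scheduled antibody measurement.
- State which outputs use the result at the visit and which use the highest on-treatment titer.

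For the HbA1c summary in 4.2.4.6 and the immune-related adverse event summaries in 4.2.4.1, keep on-treatment status as planned. Show patients positive before dosing without the required titer rise in a separate row, so that they fall in neither the treatment-emergent nor the negative group.

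If the sponsor prefers to leave out either protocol display, Section 5 should say so and give the reason.

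The Week 0 sample is already scheduled (protocol 6.2.3.1), so the cost is one derived flag and a few extra table rows. Where pre-dose positives are few or absent, the separate row will be sparse or empty, which is itself informative.
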